6.7. Continued Access to Study Intervention After the End of the Study

No study intervention will be provided to participants at the end of their study participation.

6.8. Treatment of Overdose

For this study, any dose of PF-07853578 greater than 500 mg within a 24-hour time period will be considered an overdose.

There is no specific treatment for an overdose.

In the event of an overdose, the investigator or treating physician should:

1. Contact the study medical monitor within 24 hours.
2. Closely monitor the participant for any AEs/SAEs and laboratory abnormalities as medically appropriate and follow up until resolution, stabilization, the event is otherwise explained, or the participant is lost to follow-up (as defined in [Section 7.3](#)).
3. Document the quantity of the excess dose as well as the duration of the overdose in the CRF.
4. Overdose is reportable to Pfizer Safety only when associated with an SAE.
5. Obtain a blood sample for PK analysis within 2 days from the date of the last dose of study intervention if requested by the study medical monitor (determined on a case-by-case basis).

Decisions regarding dose interruptions or modifications will be made by the investigator in consultation with the study medical monitor as needed based on the clinical evaluation of the participant.

6.9. Prior and Concomitant Therapy

PF-07853578 is primarily metabolized by [CCI](#). Therefore, use of prescription or nonprescription drugs and dietary and herbal supplements that are moderate or strong [CCI](#) inducers or inhibitors are prohibited within 14 days plus 5 half-lives prior to the first dose of study intervention. Use of all other prescription or nonprescription drugs and dietary and herbal supplements are prohibited within 7 days or 5 half-lives (whichever is longer) prior to the first dose of study intervention.

A non-exhaustive list of excluded moderate or strong CCI inducers or inhibitors is in [Appendix 9](#). Because this is not an all-inclusive list, site staff should consult with the sponsor or designee with any questions regarding potential DDI.

Limited use of nonprescription medications that are not believed to affect participant safety or the overall results of the study may be permitted on a case-by-case basis following approval by the sponsor. Acetaminophen/paracetamol may be used at doses of ≤ 1 g/day.

Females taking HRT may be eligible to participate in this study if they are willing to discontinue therapy at least 28 days prior to the first dose of study treatment and remain off hormonal therapy for the duration of the study.

All concomitant treatments taken during the study must be recorded with indication, daily dose, and start and stop dates of administration. All participants will be questioned about concomitant treatment at each clinic visit.

Treatments taken within 28 days before the first dose of study intervention will be documented as a prior treatment. Treatments taken after the first dose of study intervention will be documented as concomitant treatments.

7. DISCONTINUATION OF STUDY INTERVENTION AND PARTICIPANT DISCONTINUATION/WITHDRAWAL

7.1. Discontinuation of Study Intervention

It may be necessary for a participant to permanently discontinue study intervention. Reasons for permanent discontinuation of study intervention include the following: AEs or other (administrative) reasons.

Discontinuation of study intervention does not represent withdrawal from the study. If study intervention is permanently discontinued, the participant should remain in the study to be evaluated for ongoing AEs. See the [SoA](#) for data to be collected at the time of discontinuation of study intervention and follow-up for any further evaluations that need to be completed.

In the event of discontinuation of study intervention, it must be documented on the appropriate CRF/in the medical records whether the participant is discontinuing further receipt of study intervention or also from study procedures, further study follow-up, and/or future collection of additional information.

7.1.1. Potential Cases of Acute Kidney Injury

Participants exposed to IMP demonstrating transient or sustained increase in Screat (with decrease in Screat-based eGFR or eCrCl) require expedited evaluation to differentiate AKI from DICI. DICI is defined as transporter-mediated effect related to altered renal tubular creatinine handling without histological injury.

AKI may be due to one or more types of injury, including DIKI. Differentiation of DIKI from other causes of AKI and from DICl may require clinical, radiographic, histopathologic, and laboratory assessments, as well as nephrology consultation.

Follow-up Assessments

The participant should return to the site for evaluation as soon as possible, preferably within 48 hours of awareness of the abnormal results.

Evaluation should include physical examination, laboratory tests, detailed medical and surgical history, review of all medications (including recreational drugs and supplements [herbal]), family history, sexual history, travel history, blood transfusion, and potential occupational exposure to chemicals.

Laboratory assessments should include simultaneous serum cystatin C (Scys) and serum creatinine (Screat) tests. Estimates of eGFR, eCrCl and Screat-based eGFR and combined Screat-Scys-based eGFR should also be derived using the appropriate equation described in [Appendix 7](#).

Assessments of urine albumin-to-creatinine ratio or urine volume may also be performed as appropriate.

Differentiating Acute Kidney Injury from DICl

A confirmed Screat increase is defined as:

- (i) $\geq 0.3 \text{ mg/dL} (\geq 26.5 \mu\text{mol/L})$ within 48 hours OR
- (ii) confirmed Screat increase ≥ 1.5 times baseline (known or suspected to have occurred within the prior 7 days).

Based on the assessments performed, suspected AKI (including DIKI) may be differentiated from DICl as follows.

Adult participants

	AKI (including DIKI) Any one of the below	DICI
Scys & Screat	Simultaneous, confirmed serum cystatin C (Scys) increase and confirmed Screat increase	Confirmed Screat increase without confirmed increase in reflex Scys AND Confirmed Screat-based eGFR decrease without confirmed combined Screat-Scys-based eGFR decrease.
eGFR	Decrease in Screat-based eGFR and combined Screat-Scys-based eGFR (when available)	

	AKI (including DIKI) Any one of the below	DICI
Albuminuria or proteinuria	Confirmed albuminuria increase (see Appendix 7 for Grades A1 to A3 quantitation)	
Urine volume	Urine volume <0.5 mL/kg/h for 6 consecutive hours	

Regardless of the presence or absence of increase in Scr, DIKI and other causes of AKI may be suspected if either there is new-onset or worsening albuminuria or proteinuria are detected.

All confirmed cases of clinically relevant decrease in kidney function should be considered potential cases of DIKI if no other reason for the kidney function abnormalities has been found.

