10.7. Appendix 7: Kidney Safety: Monitoring Guidelines

10.7.1. Laboratory Assessment of Change in Kidney Function and Detection of Kidney Injury

Standard kidney safety monitoring requires assessment of baseline and postbaseline Screat measurement to estimate kidney function [Screat-based eGFR] or creatinine clearance [eCrCl]. Obtaining Screening or Baseline Scys and postbaseline reflex Scys (if confirmed Screat increase ≥ 0.3 mg/dL) makes it feasible to distinguish AKI from DICI. If Screat increase is confirmed after baseline, then reflex measurement of Scys is indicated:

ADULTS: Currently, 2021 CKD-EPI eGFR equations (Screat-only based and combined Screat plus Scys-based) are valid for use in adults only. At baseline Screat and Scys values are needed to calculate 2021 CKD-EPI eGFR by Screat-only based equation (see Table in Section 10.7.2.1) and by combined Screat plus Scys-based equation. When post-baseline Screat increase ≥ 0.3 mg/dL is confirmed, then reflex Scys measurement is needed to enable post-baseline comparison of eGFR changes (Screat-only based eGFR and combined Screat plus Scys eGFR).

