10.7.2. Age-Specific Kidney Function Calculation Recommendations

10.7.2.1. Adults (18 Years and Above) – 2021 CKD-EPI Equations

eGFR (mL/min/1.73m²)[18]

2021 CKD-EPI Screat Only	Screat (mg/dL)	Scys (mg/L)	Recommended eGFR Equation
Female	if ≤ 0.7	NA	$eGFR = 143 \times (Screat/0.7)^{-0.241} \times (0.9938)^{Age}$
Female	if > 0.7	NA	$eGFR = 143 \times (Screat/0.7)^{-1.200} \times (0.9938)^{Age}$
Male	if ≤ 0.9	NA	$eGFR = 142 \times (Screat/0.9)^{-0.302} \times (0.9938)^{Age}$
Male	if > 0.9	NA	$eGFR = 142 \times (Screat/0.9)^{-1.200} \times (0.9938)^{Age}$
2021 CKD-EPI Screat-Scys Combined	Screat (mg/dL)	Scys (mg/L)	Recommended eGFR Equation
Female	if ≤ 0.7	if ≤ 0.8	$eGFR = 130 \times (Screat/0.7)^{-0.219} \times (Scys/0.8)^{-0.323} \times (0.9961)^{Age}$
Female	if ≤ 0.7	if > 0.8	$eGFR = 130 \times (Screat/0.7)^{-0.219} \times (Scys/0.8)^{-0.778} \times (0.9961)^{Age}$
Female	if > 0.7	if ≤ 0.8	$eGFR = 130 \times (Screat/0.7)^{-0.544} \times (Scys/0.8)^{-0.323} \times (0.9961)^{Age}$
Female	if > 0.7	if > 0.8	$eGFR = 130 \times (Screat/0.7)^{-0.544} \times (Scys/0.8)^{-0.778} \times (0.9961)^{Age}$
Male	if ≤ 0.9	if ≤ 0.8	$eGFR = 135 \times (Screat/0.9)^{-0.144} \times (Scys/0.8)^{-0.323} \times (0.9961)^{Age}$
Male	if ≤ 0.9	if > 0.8	$eGFR = 135 \times (Screat/0.9)^{-0.144} \times (Scys/0.8)^{-0.778} \times (0.9961)^{Age}$
Male	if > 0.9	if ≤ 0.8	$eGFR = 135 \times (Screat/0.9)^{-0.544} \times (Scys/0.8)^{-0.323} \times (0.9961)^{Age}$
Male	if > 0.9	if > 0.8	$eGFR = 135 \times (Screat/0.9)^{-0.544} \times (Scys/0.8)^{-0.778} \times (0.9961)^{Age}$

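### When cystatin C is unchanged, the Section 7.1.1 table does not separate a benign creatinine increase (DICI) from AKI, because creatinine alone lowers the combined eGFR

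*Protocol*

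**What the plan says.** Protocol Section 7.1.1 states that "DICI is defined as transporter-mediated effect related to altered renal tubular creatinine handling without histological injury". Its table for adults has two columns.

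- The AKI column is headed "AKI (including DIKI) Any one of the below". Its rows are a simultaneous confirmed rise in Scys and serum creatinine (Screat), an eGFR row, a confirmed albuminuria increase, and low urine volume. The eGFR row reads "Decrease in Screat-based eGFR and combined Screat-Scys-based eGFR (when available". It has no size threshold and does not ask for confirmation.
- The DICI column has two limbs joined by AND. The first is "Confirmed Screat increase without confirmed increase in reflex Scys". The second is "Confirmed Screat-based eGFR decrease without confirmed combined Screat-Scys-based eGFR decrease".

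A confirmed Screat increase is defined as at least 0.3 mg/dL within 48 hours, or at least 1.5 times baseline. No such definition is given for Scys or for eGFR.

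Section 10.7.2.1 prints the equations, including the block "2021 CKD-EPI Screat-Scys Combined". Section 10.7.1 says that measuring Scys at screening or baseline, and again as a reflex test, "makes it feasible to distinguish AKI from DICI". It treats baseline Scys as needed for the calculation, whereas footnote a to Table 5 (Section 10.2) only recommends it.

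Section 7.1.1 ends by saying that confirmed, clinically relevant decreases in kidney function "should be considered potential cases of DIKI if no other reason for the kidney function abnormalities has been found".

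**The concern.** A pure effect on tubular creatinine handling raises creatinine and leaves cystatin C alone. That is the one pattern the DICI column exists to recognise. Yet the second DICI limb and the AKI eGFR row both depend on a combined eGFR that itself contains creatinine. The benign pattern therefore appears to satisfy an AKI row and to fail the DICI column.

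Safety is the primary objective, and about 6 participants receive active drug at each dose level (Section 9.5). In a dataset of that size, one or two creatinine-handling cases recorded as suspected AKI or potential DIKI could colour the early renal profile of the compound.

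**Working it through.** The plan gives no figure on this point to reproduce. The check uses the equations as printed in Section 10.7.2.1.

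**Inputs.** Screat exponents in the combined equation: −0.144 (men, Screat at or below 0.9 mg/dL), −0.219 (women, at or below 0.7), −0.544 (either sex, above the cut-point). Scys exponents: −0.323 (at or below 0.8 mg/L) and −0.778 (above). Triggers: +0.3 mg/dL or ×1.5. Eligibility: Screat-based eGFR of at least 75 (exclusion criterion 7).

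**Step 1: direction.** With Scys fixed, the constant, age and Scys terms cancel in the ratio of post-dose to baseline combined eGFR. With k the sex cut-point, s0 and s1 the two creatinine values, and a0 and a1 the exponents that apply to them:

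ratio = (s1/k)^a1 ÷ (s0/k)^a0

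Every exponent is negative and the branches meet at k, so any rise in creatinine gives a ratio below 1.

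**Step 2: size at the trigger.**
- Smallest fall, men staying at or below 0.9: 1 − 1.5^−0.144 = 5.7%.
- Largest fall, starting at or above the cut-point with ×1.5: 1 − 1.5^−0.544 = 1 − 0.802 = 19.8%.
- Across the cut-point, man 0.7 to 1.0: (1.0/0.9)^−0.544 ÷ (0.7/0.9)^−0.144 = 0.944 ÷ 1.037 = 0.911, a fall of 8.9%.

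One full substitution, for a man aged 40 with Scys 0.8 and Screat 0.9 to 1.2: before, 135 × 0.9961^40 = 115.5; after, 115.5 × (1.2/0.9)^−0.544 = 115.5 × 0.855 = 98.7.

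| Age 40 | Scys | Screat-only eGFR | Combined eGFR | Scys fall needed to cancel it |
|---|---|---|---|---|
| Man, 0.9 to 1.2 | 0.8 | 110.7 to 78.4 (−29.2%) | 115.5 to 98.7 (−14.5%) | 38% |
| Man, 1.0 to 1.3 | 0.9 | 97.6 to 71.2 (−27.0%) | 99.5 to 86.3 (−13.3%) | 24% |
| Woman, 0.7 to 1.0 | 0.8 | 111.5 to 72.7 (−34.8%) | 111.2 to 91.6 (−17.6%) | 45% |
| Man, 0.6 to 0.9 | 0.9 | 125.1 to 110.7 (−11.5%) | 111.7 to 105.4 (−5.7%) | 7% |

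A grid of 1,044 scenarios (both sexes; ages 18, 40 and 65; eligible baseline Screat from 0.40 mg/dL; Scys 0.6 to 1.1 mg/L; a rise of exactly +0.3 or ×1.5) gave a combined fall in every one, from 5.7% to 19.8%. Screat-only eGFR fell by 9.3% to 38.5%. To prevent any combined fall, Scys would have to drop by 7% to 49%.

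**Step 3: could measurement noise hide the fall?** The documents give no within-person variability for Scys, so a CV of 3%, 5%, 7% or 10% at each of two measurements is assumed. With f the Scys fall needed, the chance is Φ(ln(1 − f) ÷ (√2 × CV)). At typical baselines (age 40; men 0.8 to 1.0, women 0.6 to 0.8 mg/dL; Scys 0.8 to 0.9) f is at least 20%, and the chance is at most <0.01%, 0.07%, 1.2% or 5.6%. In the most favourable corner (men with low Screat, Scys above 0.8) it is at most 3.8%, 14%, 22% or 30%.

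**Step 4: run the creatinine-only case through the table.**
- *Confirmed means seen again on repeat.* AKI eGFR row: met. DICI limb 1: met. DICI limb 2: failed, because a repeat with unchanged Scys shows the same fall. Result: AKI only.
- *Confirmed means a fall of at least some size, say 20%.* The AKI row has no threshold and is still met. The first three table cases now also meet both DICI limbs, so they sit in both columns. In the fourth, the Screat-only fall of 11.5% would itself miss a 20% threshold applied to both eGFRs, so limb 2 still fails.
- *No combined value exists.* Read literally, the phrase about availability lets a Screat-only eGFR decrease meet the AKI row.

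**The case against.** A reader might infer more: that every benign creatinine rise is forced into the AKI column, that the primary safety conclusion would then be wrong, and that the 50% laboratory criterion in Section 6.6.1 could be tripped. The documents do not support that.

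- The table is permissive. Section 7.1.1 says the two conditions may be differentiated in this way, and that clinical, radiographic and histopathologic assessment and nephrology consultation may be needed.
- The step to potential DIKI is limited to confirmed, clinically relevant decreases with no other reason found. A creatinine-handling effect could be such a reason.
- The SAP never uses the AKI or DICI label. Sections 3.1.2 and 6.1.2 assess laboratory data against sponsor standards and summarise them by dose and treatment.
- Section 6.6.1 asks for similar clinically significant abnormalities in the same organ class that indicate dose-limiting intolerance. It does not refer to the table.
- Section 7.1.1 attaches no mandatory withdrawal to the AKI column, unlike the ECG rule in Section 7.1.2. Expedited evaluation follows a creatinine increase before any label is given.

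All of this stands and limits the consequence. The error is also in the cautious direction.

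The best technical defence is that confirmed is defined by size for Screat, so a size reading for eGFR is plausible. Section 10.7.1 also speaks of comparing the two eGFR changes, and the combined value does fall less than the Screat-only one. But the table asks only whether a decrease occurred, and no size is written down. Supplying one exchanges an empty DICI column for overlapping columns, which still do not discriminate.

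**Conclusion.** The point holds in limited form. With Scys unchanged or higher, a qualifying creatinine rise always lowers the combined eGFR under the protocol's equations, by about 6% to 20% when the rise just meets the trigger and by more for larger rises. The case then meets the AKI eGFR row. Whether it also reaches the DICI column depends on an undefined word, and neither reading gives a clean separation.

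The direction is exact algebra. The percentages assume a rise exactly at the trigger and constant Scys. The noise figures rest on assumed CVs, and a chance fall in measured Scys can occasionally leave the combined value undiminished.

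The consequence is possible mislabelling of a benign creatinine change as suspected AKI or potential DIKI in a small first-in-human safety dataset. It is not a demonstrated error in the primary conclusion and not a trigger of the stopping rule. It is worth correcting because the table fails in the case it was written to identify.

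**What to change.** Reconcile these places in a protocol amendment:

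1. Align the AKI eGFR row and the second DICI limb in Section 7.1.1 with the equations in Section 10.7.2.1, so that a creatinine-only change cannot by itself satisfy the AKI row or defeat the DICI column.
2. State what confirmed means for Scys and for each eGFR, and whether the AKI eGFR row also needs it.
3. State how the eGFR row is read when no combined value exists.
4. Reconcile Section 10.7.1, where baseline Scys is needed, with footnote a to Table 5, where it is recommended.

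The clinical criterion is for the sponsor's medical team to choose; none is proposed here. The cost is the wording of one table and a few linked sentences. If baseline Scys becomes a requirement, there is also one assay per participant. Table 5 already lists it under chemistry, and the laboratory should confirm that the planned draw covers it.

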7.1.2. ECG Changes

A participant who meets either of the following bulleted criteria based on the average of triplicate ECG readings will be withdrawn from the study intervention.

- QTcF >500 msec.
- Change in QTcF from baseline >60 msec and QTcF >450 msec.

If a clinically significant finding is identified (including, but not limited to, changes from baseline in QTcF after enrollment), the investigator or qualified designee will determine if the participant can continue in the study and if any change in participant management is needed. This review of the ECG printed at the time of collection must be documented. Any new clinically relevant finding should be reported as an AE.

7.1.3. COVID-19

If a participant has COVID-19 during the study, this should be reported as an AE or SAE (as appropriate) and appropriate medical intervention provided. Study treatment should continue unless the investigator/treating physician is concerned about the safety of the participant, in which case temporary or permanent discontinuation may be required.

It is recommended that the investigator discuss temporary or permanent discontinuation of study intervention with the study medical monitor.

7.2. Participant Discontinuation/Withdrawal From the Study

A participant may withdraw from the study at any time at their own request. Reasons for discontinuation from the study include the following:

- Refused further study procedure;

- Lost to follow-up;
- Death;
- Study terminated by sponsor;
- Discretion of the investigator or sponsor for safety or behavioral reasons, or the inability of the participant to comply with the protocol required schedule of study visits or procedures.

At the time of discontinuing from the study, if possible, an early discontinuation visit should be conducted. See the [SoA](#) for assessments to be collected at the time of study discontinuation and follow-up and for any further evaluations that need to be completed.

The early discontinuation visit applies only to participants who are enrolled/randomized and then are prematurely withdrawn from the study. Participants should be questioned regarding their reason for withdrawal.

The participant will be permanently discontinued from the study intervention and the study at that time.

If a participant withdraws from the study, they may request destruction of any remaining samples taken and not tested, and the investigator must document any such requests in the site study records and notify the sponsor accordingly.

If the participant withdraws from the study and also withdraws consent (see Section 7.2.1 for disclosure of future information, no further evaluations will be performed and no additional data will be collected. The sponsor may retain and continue to use any data collected before such withdrawal of consent.

7.2.1. Withdrawal of Consent

Participants who request to discontinue receipt of study intervention will remain in the study and must continue to be followed for protocol-specified follow-up procedures. The only exception to this is when a participant specifically withdraws consent for any further contact with them or persons previously authorized by the participant to provide this information. Participants should notify the investigator in writing of the decision to withdraw consent from future follow-up, whenever possible. The withdrawal of consent should be explained in detail in the medical records by the investigator, as to whether the withdrawal is only from further receipt of study intervention or also from study procedures and/or posttreatment study follow-up, and entered on the appropriate CRF page. In the event that vital status (whether the participant is alive or dead) is being measured, publicly available information should be used to determine vital status only as appropriately directed in accordance with local law.

7.3. Lost to Follow-Up

A participant will be considered lost to follow-up if the participant repeatedly fails to return for scheduled visits and is unable to be contacted by the study site.

The following actions must be taken if a participant fails to return to the clinic for a required study visit:

- The site must attempt to contact the participant and reschedule the missed visit as soon as possible. Counsel the participant on the importance of maintaining the assigned visit schedule and ascertain whether the participant wishes to and/or should continue in the study;
- Before a participant is deemed lost to follow-up, the investigator or designee must make every effort to regain contact with the participant (where possible, 3 telephone calls and, if necessary, a certified letter to the participant's last known mailing address or local equivalent methods). These contact attempts should be documented in the participant's medical record;
- Should the participant continue to be unreachable, the participant will be considered to have withdrawn from the study.

